5.5 Unblinding of Therapy Assignments

Breaking of the blind (active or placebo), by opening an emergency envelope, is expressly forbidden except in the event of a medical emergency where the identity of the drug must be known in order to properly treat the subject. In the event of such an emergency, it is requested that the investigator make every effort to contact the Sponsor medical representative, or Sponsor project manager prior to breaking the code. In all cases, the clinical study monitor must immediately be informed of occasions where a code has been broken. Contact details of the clinical study monitor will be provided by the Sponsor prior to the start of the study and will be readily available to all relevant site personnel at all times.

The date and time of unblinding, the name of the study personnel responsible, and the reason for the unblinding must be documented in the CRF and on the document provided in the individual code-break envelope. If the code for an individual subject is broken at the site, the monitor must be notified as soon as possible. In each case where the code is broken, that subject must be excluded from the study.

After completion of the study and after the final report has been signed, all the code-break envelopes, whether opened or not, will be returned, by the clinic pharmacy staff, to the sponsor and filed in the trial master file.

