6.8 Discontinuation from Treatment or Study

Subjects are free to withdraw from the study at any time for any reason. Subjects may be withdrawn from the study at the discretion of the Investigator. Once a subject has been withdrawn from the study, they may not be re-entered. Subjects who withdraw or who are withdrawn from the study before day 21 will be replaced. Subjects who are withdrawn due to AEs will not be replaced. If a subject is discontinued from treatment or from the study, the reason for discontinuation will be collected in the eCRF.

If a subject is prematurely withdrawn from study treatment, the Investigator should make every effort to retain the subject in the study and perform all procedures scheduled for the follow-up. Any subject withdrawn from treatment due to an AE, SAE or clinically significant safety value will be evaluated by the Investigator, or a monitoring physician, and will be treated and/or followed up until the symptoms or values have either resolved or are assessed as stable by the Investigator.

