6.8.2 Individual Stopping Criteria

If an individual subject meets one or more of the following criteria the DSMB and Investigator will discuss whether the subject should be withdrawn from the study or whether dosing should be postponed until the criterion is no longer met:

- Subject develops a concurrent illness, condition or procedural complication that would interfere with the subject's continued participation
- Subject experiences a study drug-related SAE as determined by the Investigator

Subjects may also be withdrawn from the study at any time at the discretion of the Investigator for other safety or tolerability reasons or for behavioural or administrative reasons.

A subject may also withdraw from the study at any time at their own request.

If a subject is prematurely withdrawn from study treatment, the Investigator should make every effort to retain the subject in the study and to perform all procedures scheduled for the follow-up visit. Any subject withdrawn from treatment due to an AE, SAE or clinically significant abnormal laboratory test value will be evaluated by the Investigator, or a monitoring physician, and will be treated and/or followed up until the symptoms or values have either resolved or are assessed as stable by the Investigator.

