7. ADVERSE EVENTS

An AE is any untoward medical occurrence in a patient or clinical investigation subject administered a pharmaceutical product that does not necessarily have a causal relationship with this treatment. An AE can therefore be any unfavourable and unintended sign (including an abnormal laboratory finding), symptom, or disease temporally associated with the use of an IP, whether or not related to the IP.

Any pre-existing conditions or signs and/or symptoms present in a subject before the start of the study (i.e., before informed consent) should be recorded as medical/surgical history. Any medical occurrences that are new or worsened from the time of informed consent and up to and including the final visit must be reported as AEs or SAEs. All AEs and SAEs must be recorded irrespective of whether they are considered drug-related.

Subjects will be monitored throughout the study for adverse reactions to the study medications and/or procedures at each study visit. Questions will be posed in a non-leading manner so as not to bias the response. In addition to questioning at specific time points, subjects will be encouraged to report any AEs spontaneously. Subjects will also record any AEs occurring during the outpatient phase in a subject diary card. Any subject with an AE, SAE or clinically significant abnormal laboratory test value will be evaluated by the Investigator, or a monitoring physician, and will be treated and/or followed up until the symptoms or values have resolved or are assessed as stable by the Investigator. A physician, either at the Investigative site or at a nearby hospital emergency room, will administer treatment for any SAEs. Where appropriate, medical tests and examinations may be performed to ensure that an AE has fully resolved.

Adverse events and SAEs will be monitored throughout the study from the time a subject provides consent through to the final follow-up visit. Whenever possible, a specific disease or syndrome rather than individual associated signs and symptoms should be identified by the Investigator and

recorded on the subject's eCRF. However, if an observed or reported sign or symptom is not considered a component of a specific disease or syndrome by the Investigator, it should be recorded as a separate AE on the subject's eCRF.

Each AE or SAE reported will be assessed for severity and the date and time of onset (if available), relationship to dosing, duration and outcome of each event will be noted.

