2.9 Analysis Populations

2.9.1 Intent-to-Treat Analysis Set

The Intent-to-treat (ITT) Analysis Set will consist of all randomized subjects regardless of whether or not the subject received study drug.

The ITT analysis set will be used for baseline summaries and as secondary analysis set for pharmacodynamics analysis.

2.9.2 *Per-protocol Analysis Set*

The Per-protocol (PP) Analysis Set will consist of all ITT Analysis Set subjects who have no major protocol deviations and who complete the study up to the end of the post-study assessments (i.e. attended the follow-up visit).

Major protocol deviations will be identified by the sponsor and provided to the statistician in order to create the per-protocol analysis set.

The PP analysis set will be used as primary analysis set for pharmacodynamics analysis.

2.9.3 *Safety Analysis Set*

The Safety Analysis Set will consist of all subjects who receive any amount of study drug (including placebo). All safety analyses will be conducted in this population. Safety analysis will be performed according to actual treatment.

2.9.4 *Pharmacokinetic Analysis Set*

All subjects who receive any amount of study drug will be included in the formal analysis of pharmacokinetic parameters providing they have at least one evaluable pharmacokinetic sample.

All pharmacokinetic analyses will be conducted in this population.

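### Protocol 5.5 excludes from the study any subject whose code is broken, without separating dosing, scheduled follow-up and analysis, and so conflicts with the retention rules in 6.8 and 6.8.2

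*Protocol*

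**What the plan says.** **Code break.** Under Protocol 5.5, opening an emergency envelope "is expressly forbidden except in the event of a medical emergency where the identity of the drug must be known" for proper treatment. The break must be documented and the monitor told. The section then adds: "In each case where the code is broken, that subject must be excluded from the study". It does not define exclusion.

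**Retention.** For a subject prematurely withdrawn from study treatment, Protocol 6.8 says "the Investigator should make every effort to retain the subject in the study and perform all procedures scheduled for the follow-up". Section 6.8.2 repeats this almost word for word: "the Investigator should make every effort to retain the subject in the study and to perform all procedures scheduled for the follow-up visit". Section 6.8.2 also makes a study-drug-related SAE a matter for the DSMB and Investigator to discuss, with withdrawal or postponed dosing as the possible results. Section 6.8.1 lists reasons for discontinuation from the study, and a code break is not among them.

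**Follow-up of the event.** Under 6.8, a subject withdrawn from treatment because of an AE, SAE or significant safety value "will be treated and/or followed up until the symptoms or values have either resolved or are assessed as stable by the Investigator". Section 7 says the same of any subject with an AE or SAE: "treated and/or followed up until the symptoms or values have resolved or are assessed as stable by the Investigator". It sets the monitoring window from consent to the final follow-up visit.

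**Analysis sets.** Protocol 9.3.3 and SAP 2.9.3 put every dosed subject in the Safety Analysis Set, and SAP 2.9.1 puts every randomised subject in the ITT set. Neither makes an exception for unblinded subjects.

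**The concern.** Safety and tolerability are the primary endpoint. Since 5.5 allows a code break only in a medical emergency, a properly opened code marks a subject whose safety record the trial most needs in full. For that subject, 5.5 orders exclusion from the study, not merely from study drug. A site that follows it stops the scheduled visits. A site that follows 6.8 keeps them. The amount of safety data collected on the trial's most serious case would then depend on which section the site read.

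**Working it through.** No figure in the plan can be reproduced here, because the plan gives no power calculation and attaches no number to code breaks. The check sets the sections side by side and then counts what exclusion would cost.

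**Step 1. The rules compared**

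| Question | Protocol 5.5 | Elsewhere in the protocol or SAP |
|---|---|---|
| Does the subject stay in the study? | No; mandatory exclusion | Yes, by best effort, if withdrawn from treatment (6.8, 6.8.2) |
| Who decides after a drug-related SAE? | Automatic once the code is open | DSMB and Investigator discuss (6.8.2) |
| Is a code break a listed reason for leaving? | Yes, in effect | Not listed (6.8.1) |
| Is the event followed to resolution or stability? | Silent | Yes (6.8, 6.8.2, 7) |
| Does the subject stay in the safety analysis? | Silent | Yes (Protocol 9.3.3, SAP 2.9.3) |

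The first three rows conflict. The last two do not, because 5.5 says nothing that displaces the other sections.

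**Step 2. When the conflict applies.** The retention rule covers subjects withdrawn from study treatment. Exclusion from the study during the dosing period necessarily ends treatment, so the rule is triggered. After the last dose (Day 19 in Cohorts 1-3, Day 11 in Cohort 4) there is no treatment left to stop. From then on, the tension is with section 7, which monitors AEs up to the final visit.

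**Step 3. What is lost if 5.5 prevails.** Inputs are Protocol Tables 1 and 2.

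- *Laboratory tests* (a primary endpoint component): after dosing starts there is one full assessment, on Day 21 in Cohorts 1-3 and Day 13 in Cohort 4. The Cohort 4 Day 0 entry is an alcohol and drug screen only. A subject excluded earlier has no scheduled post-dose result.
- *Visual field, Cohort 4*: the only post-dose test is on Day 13.
- *Physical examination, Cohort 4* (also a primary endpoint component): the only one after screening is on Day 20.
- *Visits, Cohort 4*: seven are scheduled from Day 0 (Days 0, 1, 2, 7, 11, 13, 20). Exclusion after Day 1 loses 7 − 2 = 5 of them, after Day 7 loses 7 − 4 = 3, and after Day 11 loses 7 − 5 = 2.

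Missing values are not imputed (Protocol 9.8, SAP 2.7), and the DSMB works from ophthalmic examinations and AEs (Protocol 10.2). The gaps would therefore stay gaps.

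**Step 4. Size.** Planned active arms are 6 in each of Cohorts 1-3 and 14 in Cohort 4. The totals agree with the plan: 3 × (6 + 2) = 24 and 14 + 7 = 21. One subject is 1/6 = 16.7% or 1/14 = 7.1% of the arm. Without that subject's post-dose laboratory result, the arm has 5/6 = 83.3% or 13/14 = 92.9% of its planned results.

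**The case against.** The strongest reply is that little is actually lost. The emergency is treated and followed under 6.8, 6.8.2 and 7 whether or not the code was opened, and the subject's recorded events are analysed. That stands, and it rules out two stronger readings a reader might infer: that the subject disappears from all follow-up, and that the event disappears from the results. On the second reading, 1/14 (7.1%) in Cohort 4 would become 0/13 (0%). It would require dropping a dosed subject from the safety analysis, which Protocol 9.3.3 and SAP 2.9.3 do not allow.

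A second reply is that 5.5 can be read as a specific exception to a general, best-effort retention rule, and that the physician-decision entry in 6.8.1 could cover a code break. So strict logical impossibility is not shown. The difficulty remains, however. If 5.5 is the exception, the retention rule fails for this subject. If 6.8 governs, the sentence in 5.5 has no effect. A physician decision is also discretionary, whereas 5.5 is mandatory.

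A third reply is that the sentence also catches accidental breaks, and that an emergency need not be drug-related. Both are true, so the rule does not select purely on drug toxicity. But the only permitted trigger is still a medical emergency.

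Loss of per-protocol status under SAP 2.9.2 is a weak argument for change. Pharmacodynamics are secondary and also tabulated in the ITT set (SAP 7.1), and the sponsor might class the break as a major deviation in any case.

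**Conclusion.** The point holds as a conflict between Protocol 5.5 and sections 6.8, 6.8.1 and 6.8.2. If 5.5 is followed, it costs the subject's remaining scheduled safety and ophthalmic assessments, the only full post-dose laboratory visit if exclusion comes before it, and the detection of new AEs at those visits. It does not cost follow-up of the event itself or membership of the Safety Analysis Set.

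The size is one subject per code break: 7.1% of the Cohort 4 active arm or 16.7% of an active arm in Cohorts 1-3. This rests on three assumptions:

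- The arms are at their planned size. SAP 2.11 reports that Cohort 3 was stopped prematurely and that Cohort 4 started recruiting in May 2021, so the Cohort 4 figure is the more relevant one looking forward.
- The code break falls in an active subject. The documents give no expected number of breaks, so no probability is attached.
- The laboratory days are as the schedule tables read. In Table 1 the last pharmacokinetic mark stands in the same Day 21 column, although its footnote dates that sample to Day 19, so the column should be checked. The conclusion needs only that there is a single post-dose laboratory visit.

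**What to change.** Replace the exclusion sentence in Protocol 5.5 with wording that agrees with 6.8, for example:

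*A code break does not by itself end study follow-up; every effort is made to complete the remaining scheduled safety assessments, the subject stays in the ITT and Safety Analysis Sets, and the code break is documented as required above.*

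An emergency break that 5.5 itself permits should not be labelled a protocol deviation; the documentation already required is enough. No rule on continuing study drug is proposed here. Sections 5.5, 6.8, 6.8.1 and 6.8.2 must be reconciled on that point by those responsible for the protocol.

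The cost is one sentence and no visits beyond those already scheduled. The Safety and ITT set definitions in the SAP need no change.

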5.6 Adherence

Cohorts 1-3:

During dosing on Days 0, 8 and 9 of the study, hospital staff or study personnel will administer all doses of study drug. The date and time of each dose will be recorded in the electronic case report form (eCRF).

During dosing on Days 10–19 of the study, the subject will self-administer all doses of study drug. The date and time of each dose will be recorded in a diary card and will be transcribed by site staff into the eCRF. Subjects will be counted as compliant with the study if they receive at least 90% of the scheduled doses during Days 9–19.

Cohort 4:

First dosing on Day 0 and 1 will be performed by hospital staff or study personnel. The date and time of each dose will be recorded in the electronic case report form (eCRF).

All other doses will be self-administered by the subjects. The date and time of each dose will be recorded in a diary card and will be transcribed by site staff into the eCRF. Subjects will be counted as compliant with the study if they receive at least 90% of the scheduled doses during Days 0–11.

5.7 Occupational Safety

PP-001 is not expected to pose any occupational safety risk to site staff under normal conditions of use and administration.

A Material Safety Data Sheet describing occupational hazards and recommended handling precautions either will be provided to the Investigator, where this is required by local laws, or is available upon request from Panoptes Pharma GesmbH.

In line with good handling of chemical products, precautions are to be taken to avoid eye contact. In the case of unintentional occupational exposure, any signs or symptoms should be treated appropriately and the Sponsor notified.

6. STUDY ASSESSMENTS AND PROCEDURES

A schedule of study procedures is presented in Table 1 and Table 2. Subjects meeting the eligibility criteria listed in Section 4 may be enrolled in the study after the nature and purpose of the protocol have been explained and written informed consent to participate has been voluntarily given. Study personnel must complete all screening procedures after informed consent is signed and before the first dose of study drug.

The day on which PP-001 is first administered will be regarded as 0 h on Day 0. The Investigator should make every effort to perform procedures at the scheduled times and to record the actual time of the procedures, where appropriate, in the subject's eCRF.

For subjects who are screened (i.e., those with signed written informed consent) but do not meet the screening criteria, the reason for screening failure will be recorded.

6.1 Safety Assessments

6.1.1 Medical and Ophthalmic History

A medical and ophthalmic history will be taken at the times outlined in the Time and Events table (Table 1 and Table 2). All medical history findings that have been present/active within 5 years before enrolment will be entered into the eCRF regardless of clinical relevance or presence at study start. Medical history findings that have not been present within the 5 years before enrolment will be recorded if deemed clinically relevant by the Investigator to the conduct of the study. The medical history should include drug allergy history and past and present smoking status.

6.1.2 Vital Signs

Vital signs (heart rate [HR] and blood pressure [BP]) will be recorded at the times outlined in the Time and Events table (Table 1 and Table 2). Blood pressure and HR will be assessed after the subject has been in a sitting position for 10 minutes. Study personnel will record vital signs measurements in the eCRF.

Vital signs measurements are to be repeated if clinically significant changes or machine errors occur. Out of range measurements (according to site normal ranges) will be repeated at the Investigator's discretion. Sitting BP and HR will be measured more frequently if warranted by the clinical condition of the subject.

6.1.3 Physical Examination

A complete physical examination will be performed by the Investigator at the times outlined in the Time and Events table (Table 1 and Table 2). This should include a review of the head, ears, nose, throat, skin, thyroid, neurological system, lungs, cardiovascular system, lymph nodes and extremities.

Body weight and height will be measured at Screening only.

6.1.4 Electrocardiogram

Triple 12-lead electrocardiograms (ECGs) will be performed within a 5-minute interval at the time points outlined in Table 1 and Table 2.

The patient should be stabilized in a supine position for 5 minutes before recording the ECG at Screening. The ECG recordings should allow a full assessment of QT intervals. Machine-read values for QTc/QTcF will be evaluated for determination of eligibility at Screening. If the quality of the ECG is insufficient then it must be repeated. All ECG data must be reviewed by the attending physician. Subject with findings of clinical significance will not be eligible to participate in the clinical study.

6.1.5 Clinical Laboratory Tests

Safety laboratory tests will be performed at the times outlined in the Time and Events table (Table 1 and Table 2) and sent to a local laboratory or evaluated at the clinical site, if appropriate. Additional tests may be performed at the discretion of the Investigator if deemed clinically appropriate. If required, samples may be sent to a central laboratory for confirmation of local results.

A full list of the clinical laboratory tests that will be performed and analysed is presented in Section 21.1.

Any clinical significant safety laboratory results outside the normal range will be repeated at the discretion of the Investigator and will be evaluated by the Investigator or designee as “clinically significant (CS)” or “not clinically significant (NCS).” Any CS value occurring during the study period should be repeated as necessary and followed until resolution.

6.1.6 Urine Pregnancy Test

Urine samples should be collected from women of child-bearing potential at the times outlined in the Time and Events table (Table 1 and Table 2). Urine pregnancy tests should be performed according to the site’s standard procedures.

Any woman with a positive pregnancy test should be withdrawn from the study and the Sponsor notified as outlined in Section 7.4.

6.1.7 Evaluation of Ocular Discomfort

An evaluation of ocular discomfort will be performed by the Investigator at the times outlined in the Time and Events table (Table 1 and Table 2). A global ocular discomfort score will be determined using a 100 mm VAS on which 0 means no symptoms and 100 means the worst possible discomfort. The following symptoms will be assessed:

Burning
Stinging
Itching
Foreign body sensation
Blurred vision

6.2 Sample Collection for Pharmacokinetic Analysis

6.2.1 Plasma Sample Collection

Blood samples for pharmacokinetic analysis of PP-001 in plasma following dosing will be collected at the times outlined in the Time and Events table (Table 1).

Blood samples will be collected into tubes containing tri-potassium ethylenediaminetetraacetic acid, immediately chilled on crushed ice, and then centrifuged at approximately 2000 g for approximately 10 minutes at +4°C to separate plasma. Following centrifugation, plasma specimens will be transferred as 2 equal aliquots (aliquot A and B) in microtubes. Plasma tubes have to be

labelled at least with the following information: PP-001-1101, subject number, sample ID (day 0, predose; day 0, 30 min; day 0, 60 min; day 8; day 19), aliquot ID (A or B). Promptly following centrifugation, plasma samples will be immediately frozen and stored at -20°C or cooler until transported. The total time from blood withdrawal to storage of plasma at -20°C should not exceed 60 minutes. The primary samples (aliquot A) will be transferred on dry ice to A&M GmbH for analysis.

